2.1 Eligibility Assessment and Informed Consent/Assent

A child is considered for the study after undergoing a routine eye examination (by a study investigator as part of standard care) where an IXT is identified and the child appears to meet the eligibility criteria for enrollment. The study will be discussed with the child's parent(s) or guardian(s) (referred to subsequently as parent(s)). Parent(s) who express an interest in the study will be given a copy of the informed consent form to read. Written informed consent must be obtained from the parent prior to performing any study-specific procedures that are not part of routine care.

Participants aged 3 to <13 years with IXT who meet all eligibility criteria will be enrolled in the study and will undergo same-day prism adaptation testing. Depending on the results of the prism adaptation test, participants will either enter the randomized trial or will end study participation. Up to 100 participants will be enrolled in the study until at least 64 have been randomized. As the randomization goal approaches, sites will be notified of the end date for enrollment. Participants whose parents have signed an informed consent form can be enrolled and potentially randomized up until the end date, which means the randomization goal might be exceeded. The maximum number of participants who will be randomized is 80.

2.2 Eligibility Criteria for Enrollment

The following criteria must be met for the child to be enrolled in the study:

Inclusion Criteria

- Age 3 to < 13 years
- Intermittent exotropia meeting all of the following criteria:
 - o Intermittent exotropia or constant exotropia at distance
 - ➤ Mean distance control score of ≥2.0 points (mean of 3 assessments over the exam) and with at least one measure of 3, 4, or 5, (spontaneous tropia) during control testing
 - o Intermittent exotropia or exophoria at near
 - ➤ Child cannot have a score of 5 points on all 3 near assessments of control
 - o Distance exodeviation at least 16Δ measured by PACT and no larger than 35Δ
 - o Near exodeviation at least 10Δ measured by PACT and no larger than 35Δ
 - \circ Near deviation does not exceed the distance deviation by more than 10Δ by PACT (convergence insufficiency-type IXT excluded)
- Distance visual acuity (by any optotype method) in both eyes according to age normal values^{27, 28} as follows:
 - o 20/50 or better for 3- to <4-year olds
 - o 20/40 or better for 4- to <5-year olds
 - \circ 20/32 or better for 5- to <7-year olds
 - 20/25 or better for ≥ 7 -year olds
- Interocular difference of distance visual acuity ≤ 2 lines (0.2 logMAR)
- Refractive error between -6.00D SE and +2.50D SE (inclusive) (based on a cycloplegic refraction performed within 7 months but prior to the day of enrollment)
- Refractive correction (pre-study spectacles) worn for at least 1 week if refractive error (based on cycloplegic refraction performed within 7 months) meets any of the following:
 - o SE anisometropia ≥1.00D

- 510 \circ Astigmatism $\geq 1.00D$ in either eye
- 511 \circ SE myopia \geq -0.50D in either eye
- If spectacles are worn, they must meet the following pre-enrollment criteria:
 - SE anisometropia corrected within <1.00D of full SE anisometropic difference
 - Astigmatism corrected within <1.00D of full magnitude; axis within 10 degrees if
 ≤1.00D of astigmatism and within 5 degrees if >1.00D of astigmatism
- Gestational age \geq 32 weeks
- Birth weight >1500 grams

514

515

523524

525

- Parent understands the protocol and is willing to accept randomization to prism spectacles or non-prism spectacles
- Parent has home phone (or access to phone) and is willing to be contacted by Jaeb Center staff and Investigator's site staff
- Relocation outside of area of an active PEDIG site within next 8 weeks is not anticipated

Exclusion Criteria

- Dissociated vertical deviation (DVD)
- Vertical deviation $>3\Delta$ in primary gaze at distance or near
- Pattern (such as an "A" or "V" pattern) with a downgaze measurement of >10Δ difference
 from straight ahead by PACT, measured by investigator's routine method
- Treatment for IXT or amblyopia (other than refractive correction) within the past 4 weeks, including vision therapy, orthoptics, patching, atropine, or other penalization
- Substantial overminus spectacles (spectacles overminused by more than 1.00D SE than the most recent cycloplegic refraction and ALSO results in minus SE power in the spectacles; i.e. underplussing is allowed) within the past 4 weeks
- Prior strabismus, intraocular, or refractive surgery (including BOTOX injection)
- Prior use of prism spectacles
- Current contact lens wear
- Abnormality of the cornea, lens, or central retina
- Down syndrome or cerebral palsy
- Developmental delay which would, in the opinion of the investigator, interfere with treatment or evaluation. Mild speech delays, reading disability, and learning disabilities are not excluded.
- Any condition that would, in the investigator's opinion, result in poor spectacle compliance
- Disease known to affect accommodation, vergence, or ocular motility such as multiple sclerosis, Graves orbitopathy, myasthenia gravis, diabetes mellitus, or Parkinson disease
- Current use of any ocular or systemic medication known to affect accommodation or vergence, such as anti-anxiety agents (e.g., Librium or Valium), anti-arrhythmic agents (e.g., Cifenline, Cibenzoline), anti-cholinergics (e.g., motion sickness patch (scopolamine)), bladder spasmolytic drugs (e.g., Propiverine), hydroxychloroquine, chloroquine, phenothiazines (e.g., Compazine, Mellaril, Thorazine), tricyclic antidepressants (e.g., Elavil, Nortriptyline, Tofranil)

- Exodeviation by PACT while wearing "trial" relieving prism is smaller at distance or near than measured during intial PACT testing (e.g. not fully adapting to prism at both distances)
- No NEW esotropia by cover test at near while wearing "trial" relieving prism
 - o An esotropia at near also present on enrollment measurement is allowed because monofixational intermittent exotropia may be associated with a small angle esotropia
- No esodeviation $>6\Delta$ on PACT at near while wearing relieving prism

554 555

556

557

558

559

560

561

2.3 **Historical Information**

Historical information elicited will include the following: date of birth, sex, race, ethnicity, cycloplegic refraction, prior treatment for IXT, spectacle correction, and medical history.

565 566 567

568

569

570

564

2.4 **Testing at the Enrollment Exam**

All testing must be performed with the participant wearing "habitual correction" (with spectacles if child currently wears spectacles or without spectacles if child is not wearing spectacles).*

571 572 573

574

575

* The exception is for a participant who does not require spectacles per IXT6 protocol but is wearing a pair of spectacles that do not meet pre-enrollment spectacle tolerances (see section 2.2). This participant can have enrollment testing performed with or without these spectacles, provided the visual acuity eligibility criteria are met (see section 2.2). If visual acuity criteria are not met, the child is not eligible at that visit.

576 577 578

There is no specified "waiting" time that needs to occur between enrollment measurements. although testing must be performed without cycloplegia and in the following specified order at the enrollment visit:

580 581

582

579

1. Spectacle Prescription Verification (Lensometry):

583 584 Prior to performing the enrollment examination, the participant's habitual spectacle correction (if worn) is to be verified using a lensometer and compared with study spectacle requirements using procedures outlined in the IXT6 Testing Procedures Manual

585 586 587

2. Symptom and Spectacle Surveys:

588 589

A brief survey of IXT symptoms will be administered to the child. Response options are based on frequency of observations: never, sometimes, and all the time.

590 591 592 • A brief survey of symptoms that may be associated with prism spectacle wear such as headaches, eye strain, and problems with spectacle wear will be administered to the parent of the participant. Parents are asked to respond to the survey questions based on their observations of their child in the past 2 weeks. Response options are based on frequency of observations: never, rarely, sometimes, often, always, and not applicable.

593 594

595

596

597

STEPS 3 through 8 must be performed in the specified order by the same study-certified examiner (pediatric ophthalmologist, pediatric optometrist, or certified orthoptist) on the same day and without cycloplegia.

- 598 3. Control of the Exodeviation #1: Control of the exodeviation will be assessed in the habitual correction*(*see above*) in primary position at distance and near using the PEDIG IXT control scale (*see below*)²⁹ and as outlined the *IXT6 Testing Procedures Manual*.
 - Distance (6 meters) fixing on an accommodative target such as a video or small letters
 - Near 1/3m (33cm)— fixing on Gulden near fixation target or similar accommodative target)
 - The scale below applies to both distance and near separately.

Intermittent Exotropia Control Scale

- 5 = Constant Exotropia
- 4 = Exotropia > 50% of the 30-second period before dissociation
- 3 = Exotropia < 50% of the 30-second period before dissociation
- 2 = No exotropia unless dissociated, recovers in >5 seconds
- 1 = No exotropia unless dissociated, recovers in 1-5 seconds
- 0 = No exotropia unless dissociated, recovers in <1 second (phoria)
- Not applicable = No exodeviation present

Directions:

601 602 603

604

605

607

608

609

610

611

612613

614

616

618

619 620

621

622

623

624

625

626 627

628

629

630

631

632

633

634

635

636

637

638

639 640

- Step1: Assessment before any dissociation: Eye alignment is observed for a 30-second period with distance fixation. The time in seconds that a spontaneous IXT is observed is counted, and the appropriate control score (3, 4, or 5) is assigned for distance fixation. This is then repeated for near fixation for another 30-second period; if an exotropia is observed, then the time in seconds that an eye is observed to be exotropic is counted and the appropriate score of 3, 4, or 5 is assigned. If a score of ≥3 is present, then Step 2 (dissociation) is not required for that test distance. First distance and then near fixation are assessed before any dissociation (i.e., before step 2).
- Step 2: Assessment with standardized dissociation is performed only if spontaneous exotropia is NOT observed during step 1 (control was not a 3, 4, or 5). Instead, control will be a 0, 1, or 2; this is determined based on the worst score determined from 3 successive 10-second periods of dissociation:
 - An occluder is placed over the right eye for 10 seconds and then removed; the length of time it takes for the re-establishment of fusion is measured in seconds.
 - The left eye is then occluded for a 10-second period (second assessment under dissociation) and after uncovering the eye, the time for re-establishment of fusion is similarly measured in seconds.
 - A third assessment is performed, by covering the eye that required the longer time to re-fuse on the first two 10-second dissociations. After uncovering the eye, the length of time it takes for the re-establishement of fusion is measured in seconds.
- The worst level of control for the three 10-second periods of dissociation by occlusion should be recorded.
- Since the control score is the slowest time of the three assessments, if a score of 2 (>5 seconds recovery) is noted on the first or second dissociation, then subsequent dissociation(s) are not needed.
- If the child has a micro-esotropia by the cover test but an exodeviation by PACT, the control scale applies to the exodeviation.

4. Stereoacuity Testing:

648

649

650

651

652

653654

655

656

657

658

659

660

661

662 663

664

665

666

667 668

669

670

671 672

673

674

675

676

677

678

679

680

681

682 683

684

685

686 687

688

689 690

691 692

693

• Stereoacuity will be assessed with habitual correction using the Randot Preschool stereotest at near (performed at 40 cm). A specific level of stereoacuity is not required for eligibility (i.e., a score of "nil" is allowed, but a child who, in the opinion of the investigator, does not understand the test would not be eligible.)

5. Control of the Exodeviation #2 (repeat) (see item #3):

• The same examiner should assess IXT control for all three assessments of control during the enrollment visit.

6. Cover Test:

- Testing must be performed by a pediatric ophthalmologist, pediatric optometrist, or certified orthoptist.
- Cover Test will be assessed in primary position at distance (6 meters) and near (1/3 m), using procedures outlined in the IXT6 Testing Procedures Manual.
- If the child has a micro-esotropia by the cover test but an exodeviation by PACT, the esodeviation will be recorded for the cover test.

7. PACT Testing & AC/A Determination:

- Testing must be performed by a pediatric ophthalmologist, pediatric optometrist, or certified orthoptist.
- PACT will be assessed in primary gaze using the IXT6-approved prism set and without cycloplegia at distance (6 meters) and near (1/3 m) in habitual correction. The procedure will include bracketing to find and record the high neutral endpoint as outlined in the IXT6 Testing Procedures Manual.
- AC/A assessment is performed by measuring the PACT at distance (6 meters) with the participant wearing -2.00D lenses over the habitual correction. The AC/A ratio is calculated automatically by the website by taking the difference between the distance PACT measurements with and without the -2.00D lenses and dividing the difference by 2.

8. Control of the Exodeviation #3 (repeat) (see item #3):

• The same examiner should assess control for all three assessments of control during the enrollment visit.

9. Fusional Convergence Amplitude Testing:

- Testing must be performed by a pediatric ophthalmologist, pediatric optometrist, or certified orthoptist using procedures outlined in the IXT6 Testing Procedures Manual.
- Fusional convergence amplitude to be measured at distance
- Using the PEDIG-approved IXT6 prism bar, record the blur, break, and recovery points according to the IXT6 Testing Procedures Manual.

10. Suppression:

• Assessment of suppression at distance using the Suppression Scale using procedures outlined in the IXT6 Testing Procedures Manual.

11. Distance Visual Acuity Testing:

 Monocular distance visual acuity testing with the habitual correction and without cycloplegia will be measured using the investigator's usual method (recognition acuity using any optotype).

12. Additional Clinical Testing:

• Ocular examination as per the investigator's clinical routine to rule out ocular abnormality or lens opacity (if not performed within 7 months)

697

698

2.5 Confirmation of Eligibility and Completion of Enrollment

Completion of enrollment will occur at the conclusion of the Enrollment Exam after confirming that all eligibility criteria are met. Participants not meeting all eligiblity criteria or who are unable to complete enrollment testing other than fusional convergence amplitude and suppression testing are not eligible for the study.

699 700 701

Eligibility criteria relating to refractive error and spectacle correction are based upon the cycloplegic refraction done within 7 months of enrollment.

702 703 704

• If all eligibility criteria are met the participant is enrolled and included in the Prism Adaptation Test Screening.

705 706 • If all eligibility criteria are not met, the participant is not enrolled or included in the Prism Adaptation Test Screening.

707 708

709

710

Prism Adaptation Test Screening 2.6

Participants who meet all enrollment criteria at the enrollment exam will undergo same-day prism adaptation testing. The results of the prism adaptation test will be used to determine eligibility for randomization.

711 712 713

714

715

716

717

2.6.1 Prism Adaptation Test

The prism adaptation test procedure is documented in the IXT6 Testing Procedures Manual.

- Testing must be performed by a pediatric ophthalmologist, pediatric optometrist, or certified orthoptist.
- Testing must be done without cycloplegia.

718 719 720 • The purpose of testing is to assess a child's initial response to the amount of relieving prism that would be prescribed if randomly assigned to the prism spectacles group (see table 1, section 3.1).

721 722 723 • The examiner will place BOTH of the following in the IXT6 approved trial frame and have the child wear it continuously for at least 30 minutes: o Trial lenses equal to the amount of refractive correction in the habitual spectacles,

724 725

or no correction if habitual lenses are not worn. o Trial prism lenses from the IXT6 trial prism set with protocol-determined amount of relieving prism (see table 1, section 3.1), with the following caveat:

726 727 728

 \triangleright To avoid the need for trial prisms of 3.5 \triangle for cases in which the total prism magnitude of 7Δ , a 4Δ prism will be placed in front of the eye that normally deviates, and 3Δ prism will be placed in front of the other eye.

729 730

• After 30 minutes of wearing the prism in trial frames, perform the following in primary position while the participant continues to wear the prism trial frames:

731 732 733

o Cover test at near PACT testing at distance and at near

734

2.7 **Eligiblity for Randomization**

735 736 737

The results of the prism adaptation test determine whether the participant is eligible for randomization or whether study participation will end.

738

Participants ARE eligible to be randomized if ALL of the following criteria are met:

739 740

• The participant has not fully adapted to prism at distance AND near

- 741 742
- 743 744 745
- 746 747
- 748 749 750
- 751 752
- 753 754
- 755 756 757 758 759
- 760 761
- 762 763 764
- 765 766 767
- 768 769 770 771
- 772 773 774 775
- 777 778 779 780

781 782 783

785 786

784

- 787
- 788

- o The participant's PACT measurement at distance while wearing "trial" relieving prism is smaller than the originally measured deviation at distance OR near when not wearing prism (i.e., at least some reduction in deviation with prism)
- The participant has no NEW near esotropia by cover test while wearing the "trial" relieving prism (e.g., a microesotropia previously noted on near cover test during initial testing and also noted at this time is allowed)
- The participant has no esodeviation $>6\Delta$ on PACT at near while wearing "trial" relieving prism

Participants who fail to meet any of the above criteria will not be randomized and will discontinue study participation.

Examples:

Consider the following participants, each with a 30Δ exodeviation measured by PACT at both distance and near. These participants are now all wearing 40% relieving prism (12Δ, with 6Δ base-in in each lens) in a trial frame with habitual refractive correction. After 30 minutes of wearing prism, the participants have their deviation measured by the PACT in primary position while wearing the trial frame including relieving prism. Post-prism adaptation PACT measures are given in the following examples:

Patient is eligible based upon prism adaption and CAN be randomized.

- 1. Example 1 No Prism Adaptation: Wearing prism, the participant now measures 18Δ exodeviation at distance by PACT and 18Δ exodeviation at near by PACT, and no esotropia by cover test at
 - near. The angle has decreased by the amount of prism given, so there is no prism adaptation.
- 2. Example 2 Partial Prism Adaptation: Wearing prism, the participant now measures 30Δ exodeviation at distance by PACT and 25Δ exodeviation at near by PACT, and no esotropia by cover test at near. The distance angle has not decreased while wearing prism but the near angle has decreased while wearing prism.
- 3. Example 3 Pre-Existing Micro-Esotropia at Near: Wearing prism, the participant measures 18Δ exodeviation at distance by PACT and 18Δ exodeviation at near by PACT, but is esotropic at near by cover test (reflecting pre-existing monofixation; where, in this case, the tropia and phoria are in the opposite direction). The esotropia was present prior to prism adaptation. The PACT angle has decreased by the amount of prism given, so there is no prism adaptation.

Patient is NOT eligible based upon prism adaption and CANNOT be randomized.

1. Example 1 - Full Prism Adaptation: Wearing prism, the participant now measures 30Δ exodeviation by PACT at distance and near with the prism in place. The patient has completely adapted to the prism and is NOT eligible due to complete prism adaptation.

- 2. Example 2 New Esotropia at Near: Wearing prism, the participant now measures 18Δ exodeviation at distance by PACT and 4Δ esodeviation at near by PACT and has an esotropia by cover test at near. The participant did not previously have an underlying esotropia. This participant is NOT eligible due to the new esotropia at near.
 - 3. Example 3 Esodeviation at Near now >6Δ by PACT:
 Wearing prism, the participant measures 18Δ exodeviation at distance by PACT and 8Δ esodeviation at near by PACT, although the participant is not esotropic at near by cover test. This participant is NOT eligible due to an esodeviation >6Δ at near by PACT while wearing prism.

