Additional Eligibility Criteria for Randomization Based on Prism Adaptation Testing

- Exodeviation by PACT while wearing "trial" relieving prism for 30 minutes is smaller at distance or near than measured during initial testing (e.g. not fully adapting to prism at both distances)
- No new esotropia on cover test at near while wearing "trial" relieving prism for 30 minutes, compared with enrollment measurement taken without prism
- No esodeviation $>6\Delta$ on PACT at near while wearing "trial" relieving prism for 30 minutes

Sample size

- 410 Up to 100 participants will be enrolled for same-day prism adaptation testing until up to 64 411 participants meeting the randomization eligibility criteria based on the prism adaptation test are 412 randomized (32 per treatment group).
- 414 Treatment Groups
- Als Randomization (1:1) to the following groups:
- Prism Group: Spectacles with refractive correction AND base-in relieving prism (40% of the greater of the exodeviation by PACT at distance or near) equally divided between the 2 lenses

• Non-prism Group: Spectacles with refractive correction (or plano spectacles if no significant refractive error) and no prism

421 422

424

Visit Schedule

- Enrollment Visit
 - If eligible, Randomization (same day as enrollment visit or within 7 days)
- 3-week phone call (21 to 28 days) after randomization
 - Outcome Exam: 8 weeks (± 2 weeks) after randomization

426 427 428

429

Testing Procedures

Distance and near control of IXT (3 measurements), near stereoacuity, distance and near cover test, and distance and near PACT will be measured by a study-qualified examiner at enrollment, and by a Masked Examiner at 8 weeks. The prism adaptation test will be assessed by a study-qualified examiner at enrollment. Distance visual acuity, fusional convergence amplitude, and suppression will be assessed by a study-qualified examiner at both visits. In addition, symptoms of headache, eye strain, dizziness, nausea, and problems with spectacle wear will be assessed at both visits.

437 438

Primary Analysis

• A comparison of mean distance control scores (mean of 3 assessments over the exam) between the prism group and the non-prism group at 8 weeks.

440 441 442

443

444

445

446

439

Secondary Analyses

- A comparison of the proportion of participants showing a "treatment response," defined as an improvement of ≥1 point in distance control (mean of the 3 assessments over the exam) between enrollment and 8 weeks.

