 - \circ 20/32 or better for 5- to <7-year olds
 - 20/25 or better for ≥ 7 -year olds
- Interocular difference of distance visual acuity ≤2 lines
- Must be wearing refractive correction (pre-study spectacles) for at least 1 week if refractive error (based on cycloplegic refraction performed within 7 months) meets any of the following:
 - o SE anisometropia ≥1.00D
 - \circ Astigmatism $\ge 1.00D$ in either eye
 - \circ SE myopia \geq -0.50D in either eye
- If spectacles are worn, they must meet the following pre-enrollment criteria:
 - o SE anisometropia corrected within 1.00D of full SE anisometropic difference
 - Astigmatism corrected within 1.00D of full magnitude; axis within 10 degrees if ≤1.00D and within 5 degrees if >1.00D
 - No overminus (i.e., no more than 1.00D more minus SE than full SE if also resultant minus SE)
 - o No overplus (i.e., no more than 1.00D more plus SE than the full SE)

Enrollment Exam Testing Procedures

- Lensometry
- Symptom survey and spectacle surveys
- IXT control assessment #1(distance and near)
- Randot Preschool stereoacuity at near
- IXT control assessment #2 (distance and near)
- Cover Test (distance and near)
- Prism and Alternate Cover Test (distance and near, distance with -2.00D lens for AC/A)
- IXT control assessment #3 (distance and near)
- Fusional convergence amplitude testing (distance)
- Suppression assessment
- Distance visual acuity (any optotype)

Participant meets all eligibility criteria AND completes all required testing

Complete Enrollment and continue to Prism Adaptation Test

Participant does NOT meet all eligibility criteria or does not complete all required testing

Do not proceed – participant not eligible

459

[figure not shown]
IXT6 Pilot Study Protocol v1.0 29May2019 29May2019 1-8

IXT6 Pilot Study Protocol v1.0

- 30 min wearing relieving prism and refractive correction in trial frames
- While wearing prism in trial frames, retest
 - Cover Test at near
 - o Prism and Alternate Cover Test (PACT) at distance and near

Are all of the following criteria met while wearing "trial" relieving prism?

- Exodeviation by PACT is smaller at distance or near than measured during initial testing
- No NEW esotropia by cover test at near
- No esodeviation $>6\Delta$ on PACT at near

8-Week (± 2 weeks) Outcome Exam

The following procedures are performed by someone other than the masked examiner:

- Lensometry
- Compliance assessment
- Symptom and spectacles surveys

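### The adaptation test in protocol 2.7 leaves out the near angle measured in prism and rejects the protocol's own eligible Example 2; SAP 5.2 then defines full adaptation in a third way

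*Protocol*

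**What the plan says.** Protocol 2.7 sets the adaptation criterion in two layers. The parent bullet reads "The participant has not fully adapted to prism at distance AND near". Its single sub-bullet makes this measurable: PACT at distance in "relieving prism is smaller than the originally measured deviation at distance OR near when not wearing prism", with the gloss "at least some reduction in deviation with prism". Section 2.6.1 has PACT in prism measured at both distance and near. Near PACT in prism re-enters 2.7 only through the separate limit on near esodeviation.

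Elsewhere the protocol words the criterion differently. In 1.15 the exodeviation in "relieving prism for 30 minutes is smaller at distance or near than measured during initial testing"; the flow chart says "Exodeviation by PACT is smaller at distance or near than measured during initial testing"; the list printed after 2.2 says the same in substance. The ancillary-study paragraph in 1.15 and section 5.6 call a child fully adapted only if there is no reduction at both distances.

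All the worked examples in 2.7 start from a 30Δ "exodeviation measured by PACT at both distance and near". Eligible Example 2 measures 30Δ at distance and 25Δ at near in prism and may be randomized. The stated reason is: "The distance angle has not decreased while wearing prism but the near angle has decreased while wearing prism".

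SAP 5.2 defines full adaptation as PACT in prism at least as large as the original at distance *and/or* near, each compared at the same testing distance. It uses the term for two results: the proportion who fully adapt and the proportion eligible for randomization.

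**The concern.** The adaptation screen exists to keep out children who fully adapt, whom protocol 1.8 expects not to benefit, while partial adapters are hypothesized to improve. Section 2.8 names 2.7 as the randomization criteria. If the measurable line in 2.7 does not match its own example, a site cannot follow both.

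The SAP wording matters separately. The proportion fully adapting is the ancillary study's main result. Under the SAP rule, a child whom the protocol randomizes as a partial adapter would be reported as fully adapted and as ineligible.

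**Working it through.** The documents give no figure to reproduce here, so the check codes each definition and runs the same children through it.

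**Notation.** oD and oN are the original PACT at distance and near; pD and pN are the values in prism; esodeviations are negative. A child is *not fully adapted* if:

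- **Rule A** (protocol 1.15, flow chart, list after 2.2, 5.6): pD < oD or pN < oN.
- **Rule B** (2.7 sub-bullet, read literally): pD < oD or pD < oN, which is the same as pD < max(oD, oN). The value pN does not appear.
- **Rule C** (SAP 5.2, *and/or* taken to include *or*): pD < oD and pN < oN.

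| Child | Before, D/N | In prism, D/N | A | B | C |
|---|---|---|---|---|---|
| Eligible Example 1 | 30/30 | 18/18 | yes | yes | yes |
| Eligible Example 2 | 30/30 | 30/25 | yes | **no** | **no** |
| Eligible Example 3 | 30/30 | 18/18 | yes | yes | yes |
| Not-eligible Example 1 | 30/30 | 30/30 | no | no | no |
| Not-eligible Example 2 | 30/30 | 18/−4 | yes | yes | yes |
| Not-eligible Example 3 | 30/30 | 18/−8 | yes | yes | yes |
| Constructed (i) | 30/30 | 18/30 | yes | yes | **no** |
| Constructed (ii) | 20/30 | 20/30 | no | **yes** | no |
| Constructed (iii) | 20/30 | 25/30 | no | **yes** | no |

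Not-eligible Examples 2 and 3 are excluded by the esotropia and esodeviation criteria, not by adaptation.

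**Worked examples.** Rule A fits 6 of 6; rules B and C fit 5 of 6, both failing on eligible Example 2. The protocol states an adaptation status for only four examples (the three eligible ones and the first not-eligible one). On those the counts are 4 of 4, 3 of 4 and 3 of 4.

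**Three distinct rules.** Example 2 separates A from B and C. Child (i) separates C from A and B.

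**The opposite error in rule B.** Section 2.2 requires only "Near deviation does not exceed the distance deviation by more than" 10Δ, so 20/30 can be enrolled. Child (ii) has no reduction at either distance, yet 20 < 30 meets the sub-bullet. Child (iii) has a larger distance angle, and 25 < 30 still meets it. Both fail the parent bullet and the gloss, so 2.7 contradicts itself; it does not plainly admit full adapters. Because every worked example has equal starting angles, none exposes this.

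**Parent bullet.** Its *AND* can mean *not adapted at both* (rule A) or *adapted at neither* (rule C). Either reading needs pN, so neither rescues the sub-bullet.

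**Effect on the screening results.** Protocol 5.6 gives N between 64 and 100. Each child reduced at exactly one distance is not fully adapted under A and fully adapted under C, so the proportion shifts by 1/N:

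- N = 100: 1/100 = 1.0 percentage point
- N = 64: 1/64 = 1.6 percentage points

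The eligible proportion falls by the same amount if the child meets the other two criteria. The share of such children is not given. If it were 5%, 10% or 20% (assumed values), the SAP estimate of full adaptation would exceed the protocol 5.6 estimate by 5, 10 or 20 points.

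**The case against.** The best reply is that the intent is easy to recover. The summary criterion, the flow chart, the list after 2.2, section 5.6 and Example 2 all agree, and the sub-bullet looks like a misplaced *at distance*. Section 2.8 also requires the 2.2 criteria, and the list printed with them would stop both 20/30 children. Child (iii) is extreme: a 30Δ maximum means 12Δ of trial prism, so 25Δ in prism implies about 25 + 12 = 37Δ of distance deviation against 20Δ before. The detailed procedure is in the Testing Procedures Manual, which is not among the documents. The primary analysis is an intent-to-treat comparison, adaptation status is not in its model, and screening precedes allocation, so the treatment comparison is not biased.

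Much of this stands. It supports reading 2.7 as a drafting slip, and it limits the 20/30 cases to showing that the sub-bullet is wrong as a rule. It does not remove the conflict over Example 2, where a literal reading refuses a child the protocol says may be randomized. Nor does it answer the SAP point: SAP 5.2 openly corrects another protocol error, about repeat testing, but does not say that it changes this definition.

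**Conclusion.** The concern holds and should be fixed. The documents carry three different rules for full adaptation. The 2.7 sub-bullet contradicts its parent bullet, its gloss, eligible Example 2 and section 5.6; the SAP wording contradicts 5.6 and Example 2. The certain size is one misclassified worked example under each of the two deviant rules, and a shift of 1.0 to 1.6 percentage points in the screening proportion for each child reduced at only one distance. The total shift cannot be determined. The conclusion rests on reading the sub-bullet literally and on *and/or* including *or*; read strictly as *and*, the SAP would match 5.6. How sites or the website applied the criterion is not in the documents.

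**What to change.** Reconcile the 2.7 sub-bullet with 1.15, the flow chart, the list after 2.2, 5.6 and the worked examples, so that PACT in prism is compared with the original at the same testing distance and both distances enter the test. Replace *and/or* in SAP 5.2 with the both-distances definition of protocol 5.6, and use that one definition for both SAP proportions. Confirm that the website eligibility logic and the Testing Procedures Manual match. A worked example with unequal near and distance angles would help but is optional.

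The cost is one sentence in the protocol, one phrase in the SAP and a logic check. Distance and near PACT in prism are already collected, so no extra testing is needed.
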